### **15.1.2 Data Acquisition and Central Study Database**

The entire study will be conducted using an electronic data acquisition method where all clinical data on enrolled subjects will be data entered (single-keyed) by the site personnel into a web-based data management system, REDCap. In order to provide user-friendly and easy-to-navigate interfaces, the REDCap data capture screens are designed based upon individual CRFs. Prior to study start, the system is validated to ensure the data entry screens mirror the CRFs and that the pre-programmed data rules appropriately detect incorrect data. The data will be managed after data entry via data queries from the MSMC.

The latest version of each CRF and source documents will be available as a PDF file on the REDCap website for use by study personnel. This process facilitates version control of these study related documents, particularly since documents may evolve over the course of the study.

This user friendly web-based database system, developed and validated by the MSMC, will be used for subject data entry, data validation, project progress monitoring, subject tracking, user customizable report generation and secure data transfer.

## **15.2 Reporting Module**

The REDCap system also has a real-time reporting component that allows authorized users to view protocol specific reports as data listings and in a summary format, overall and by site, at any time during the study via the password protected system. The Reporting Module is developed based on input from the TOC and includes reports on enrollment, SAEs, CRF processing, and subject progress. The reports will be presented to the TOC in a manner that protects the integrity of the study (e.g., blinded).

MSMC will provide the TOC and authorized study personnel access to a standard set of web-enabled tools within REDCap. These tools allow the authorized research personnel to track trial progress by reviewing accrual status and CRF status of enrolled subjects. Other assistive tools and available information includes subject enrollment logs, basic subject demographics, CRF completion rate and number of data queries outstanding and resolved.

## **15.3 Security, Privacy, and Confidentiality**

The MSMC employs several layers of data protection to ensure data security.

The first part of security is physical protection of the hardware systems employed by the MSMC. The facility housing the MSMC hardware is protected 24/7 by multiple layers of security. By limiting access, ensuring only authorized personnel have access, and tracking all entry, the risk of a security breach is minimal. All communication with the web server and client is encrypted. To help protect and secure the data stored in REDCap's back end database, the software application employs various methods to protect against malicious users who may attempt to identify and exploit any security vulnerabilities in the system. In REDCap, all incoming data gets intentionally filtered, sanitized, and escaped. Server environment variables that are vulnerable to forgery by end-users are also checked and sanitized. To specifically protect against Cross-Site Request Forgery (CSRF), which is another method of attack, REDCap utilizes a "nonce" (a secret, user-specific token) on every web form used in the application. The nonce is generated as a unique value for each new REDCap session

To maintain electronic records in the database as adequate and accurate, the REDCap system tracks all changes made to any dynamically managed electronic records. REDCap has a built-in audit trail that automatically logs all user activity and logs all pages viewed by every user, including contextual information (e.g. the project or record being accessed). The logging record can itself be viewed within a project by users that have been given privileges to view the Logging page. The Logging page allows such users to view or export the entire audit trail for that project, and also to filter the audit trail in various ways based upon the type of activity and/or user. This audit-trail information is created with a computer generated time-stamp and the user name in chronological order, when the original data is modified or deleted.

## **16. Adverse Events**

Adverse events (AEs) may occur at any time after enrollment. Pre-existing conditions will be documented in the subject's medical record as part of prior medical history but will not count against either study procedure unless there is a worsening of the condition during the study. Adverse events (serious and non-serious) will be documented on an Adverse Event CRF. Non-serious adverse events will be recorded from enrollment through hospital discharge or 7 days whichever is earlier. Serious adverse events will be recorded from enrollment through the end of study (i.e., 90 day follow-up).

Investigators will record characteristics of each adverse event on an Adverse Event CRF. Each adverse event will be judged by the Investigator as to its level of relatedness to the investigational devices and investigational procedure.

In addition, the Investigator will identify the date of onset, severity, required treatment, relatedness and duration of the event. Severity will be judged using the scale noted in Table 10. All adverse events will be monitored until they are adequately resolved or explained or until the subject reaches the end of the study.

Table 10. Definition of event severity for judgment by Investigator.

Term	Definition
Mild	Patient is aware of a sign or symptom, but that sign or symptom does not interfere with normal activity or symptom is both transient and resolved
Moderate	Symptoms interfere with the subject's usual activity or symptoms require treatment
Severe	Symptom(s) cause either severe discomfort or have a significant impact of the subject's usual activity and symptoms require treatment

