#### **4.4 Study Visits**

Subjects enrolled to this study will follow the below visits schedule according to their institutional standard of care for stroke patient follow-up.

- Pre-Treatment
- Procedure
- Post procedure (within 24 hours, Apollo / Artemis MIES patients)
- 7 days post-enrollment or Discharge (whichever comes first)
- Discharge (if beyond 7 days)
- 3 month follow-up (+/- 14 days)
- 6 month follow-up (+/- 21 days)
- 12 month follow-up (+/- 35 days)
- 

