### 5.9.2 *Cross-Sectional Imaging*

All scheduled CT and MR studies will be assessed by a central core lab neuroradiologist. The volume of hemorrhage on the diagnostic scan will be calculated using a standard  $A \times B \times C/2$  calculation. On the CT slice with the largest area of ICH, the largest diameter (A) is measured in cm. The dimension of the hemorrhage perpendicular to the largest diameter (B), represents the second diameter. The third diameter (C) will be calculated either by multiplying the number of CT slices which depict the hematoma by the slice thickness or determined on coronal or sagittal reconstructions.

Hemorrhage volumes will also be assessed using a manual volume measurement technique on the diagnostic scan and all subsequent scans, as defined in the Imaging Manual. Intraventricular hemorrhage will be assessed on each scan and graded according to a modified Graeb score (see the Imaging Manual and Manual of Procedures).

Scheduled imaging studies include the diagnostic/admission scan, the stability scan(s) (at least 6 hours after the diagnostic scan), CT or MR angiogram (with either the diagnostic or stability scan), Post-operative post-presentation scan 7 day post presentation scan.

Table 1. Schedule of Events

ACTIVITY	SCREENING /BASELINE	STABILITY SCAN (at least 6 hours post initial CT)	TREATMENT	24 hour post - MIES (+/-12)	DISCHARGE AND/OR 7 DAYS (+/- 1 day)	3 MONTHS (+/- 14 days)	6 MONTHS (+/- 21 days)	1 YEAR or END OF STUDY (+/- 35 days)
Informed Consent	X							
Inclusion/ Exclusion Criteria	X							
Medical History	X							
Focused Exam	X	X		X	X	X	X	X
Standard of Care Labs	X	X		X	X			
Standard of Care CT/MR	X	X	X		X			
CTA or MRA	X (or at stability)	X (if not done with Baseline)						
Barthel	Historic					X	X	X
NIHSS	X	X		X	X	X	X	X
GCS	X	X		X	X	X	X	X
mRS	Historic			X	X	X	X	X
Stroke Impact Scale (QOL)						X	X	X
ED-5D-5L						X	X	X
Pregnancy Test if childbearing potential	X	Or X						
Con Medications	X	X	X	X	X	X	X	X
Apollo / Artemis MIES under general anesthesia within 24 hours of sx onset			X					
Adverse Events			X	X	X	X	X	X
All brain imaging sent to central core lab	within 48 hours of test	within 48 hours of test	within 48 hours of test	within 48 hours of test	within 48 hours of test			

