### 5.9.3 *Serious Adverse Events*

All serious adverse events occurring during the 365 days of study participation will be recorded. Adverse events and serious adverse events are critical endpoints and will be assessed as they occur and at the scheduled clinic visits. A serious adverse event is one that is fatal or life-threatening, is permanently or substantially disabling, requires or prolongs hospitalization, or any event that the treating clinician judges to be a significant hazard. For each recorded serious adverse event, the patient's attending physician will be asked to classify the causal relationship of the event to the study treatment as probable, possible, unlikely, and unrelated. Detailed form and narrative reports of the following specific adverse events will be obtained:

- Death (all cause) within 90 days of enrollment
- Death within 7 days of enrollment: Immediate periprocedural death
- Symptomatic Re-Hemorrhage or New Hemorrhagic Event: any new intracranial hemorrhage or increase in size of pre-existing hemorrhage (IPH, IVH or extra-axial bleed) within 90 days associated with an increase of 4 or more points on the NIHSS or GCS increase  $\geq 2$  persisting for at least 24 hours and/or requiring emergency surgical decompression or resulting in death.
- Symptomatic Evolution of Perihematomal Edema: Edema with increased mass effect or uncontrolled ICPs within 90 days requiring emergency surgical decompression NOT related to new or increased hemorrhage (i.e. edema related) associated with an increase of 4 or more points on the NIHSS or GCS increase  $\geq 2$  persisting for at least 24 hours, and/or requiring emergency surgical decompression or resulting in death.
- Symptomatic Ischemic Stroke: A new ischemic stroke (ipsilateral, contralateral; contiguous with bleed/operative site or remote; cortical, subcortical or perforator distribution) within 90 days associated with an increase of 4 or more points on the NIHSS or GCS increase  $\geq 2$  persisting for at least 24 hours and/or requiring emergency surgical decompression or resulting in death.
- Surgical complications related to Apollo / Artemis MIES: Surgical site infection, brain abscess or confirmed meningitis, or documented complication(s) deemed specifically related to the procedural anesthetic (medication, access or intubation related) within 90 days.

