## 6. Study Primary Endpoints

The primary objective is to assess the impact of Apollo / Artemis MIES upon clinical outcomes in patients with supratentorial intracranial hemorrhage with primary endpoints defined as:

- Rate of recruitment over a two-year time span following first patient enrollment
- Rate of successful 180 day follow up obtainment.

- Statistical details can be found in section 7.2.

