### **16.2            *Reporting and Review of Adverse Events***

To provide for consistent reporting of adverse events, serious and non-serious adverse events will be recorded on the Adverse Event CRF. Non-serious adverse events will be recorded from enrollment through Day 7 or hospital discharge (whichever occurs first). Serious adverse events will be recorded from enrollment through the end of study (i.e., 90 day final follow-up visit, death, or withdrawal of consent).

In order to ensure prompt reporting of adverse events, we require that all adverse events be entered into the REDCap web-based database (REDCap) within five working days of their becoming aware of the event during the initial admission. For all serious adverse events (SAEs), we require that they be reported in the REDCap within 24 hours of the study site staff first being made aware of the occurrence of the SAE. The 24- hour reporting requirement for SAEs applies to all study phases.

Reporting of serious or life-threatening adverse events will trigger notification of the event to the Medical Monitor (MM). The MM will conduct an independent review of these specific SAE. If the MM believes the adverse event is serious, unexpected and either definitely, probably, or possibly related to the investigational device(s) and/or study procedures, the TOC staff will forward a Safety Report (pre-filled with as much data as possible) to the clinical site Investigator to be completed with any additional information that may be relevant to the SAE. The Safety Reports will be included in the reports prepared for the DSMB. The principal investigator, at each clinical site, will be responsible for reporting to his/her own IRB/EC according to individual IRB/EC policies. After the submission of the initial Safety Report, the principal investigator at the corresponding clinical site will be responsible for obtaining follow-up information about the event, in order for it to be reported it to the TOC.

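### Serious adverse events are recorded for 365 days under Section 5.9.3 but only to day 90 under Sections 16 and 16.2

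*Combined protocol and SAP*

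**What the plan says.** **The 365-day rule.** Section 5.9.3 states: "All serious adverse events occurring during the 365 days of study participation will be recorded". It adds that events are assessed both as they arise and at scheduled visits.

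**The 90-day rule.** Section 16 states: "Serious adverse events will be recorded from enrollment through the end of study (i.e., 90 day follow-up". Section 16.2 gives the same limit and describes the end of study as "i.e., 90 day final follow-up visit, death, or withdrawal of consent".

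**The schedule.** The last visit in Section 4.4 is "12 month follow-up (+/- 35 days". The last column of Table 1 (Section 5.9.2) is headed "1 YEAR or END OF STUDY (+/- 35 days", and the Adverse Events row is marked there and at 6 months. One of the primary endpoints in Section 6 is "Rate of successful 180 day follow up obtainment".

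**Related duties.**
- Sections 16 and 16.2 stop recording of non-serious events at day 7 or discharge, whichever is earlier.
- Section 16 also says: "All adverse events will be monitored until they are adequately resolved or explained or until the subject reaches the end of the study".
- Section 16.2 says of rapid reporting that the "hour reporting requirement for SAEs applies to all study phases".
- Section 5.9.1 has neurological events, serious or not, looked for at each visit; its assessments run to day 360.
- Section 8.1 requires an adverse event form when an SAE causes a missed visit.

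**The concern.** The two rules cannot both be followed. The 90-day limit is not a stray phrase in the background: it appears twice, in the two sections that site staff would consult for adverse event reporting. Both tie it to the end of the study, and Section 16.2 calls the 90-day visit the final one, although two more visits follow.

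If a site applies Sections 16 and 16.2, three things stop at day 90: SAE recording, entry in the database within 24 hours, and the notification of the medical monitor that such entry triggers. Follow-up of events not yet resolved or explained can stop there too, because Section 16 ties it to the same end of study.

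Other provisions depend on the same window. Section 7.5.2.1 has the operating committee and the DSMB receive reports of all adverse and serious adverse events, and Section 21 has every SAE verified against source. Neither has a fixed denominator while the window is undecided. With up to 10 sites free to read the protocol differently, late SAE data could be incomplete and uneven. A table showing no late SAEs could then mean that none occurred or that none were collected.

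**Working it through.** The plan gives no figure to reproduce. The check compares the passages and then measures the gap.

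**1. Which passages support which end date**

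| Place | SAE recording or follow-up implied |
|---|---|
| Section 5.9.3 | 365 days |
| Section 4.4 | Visits at 3, 6 and 12 months |
| Table 1, Adverse Events row | Marked at 3 months, 6 months and 1 year |
| Section 5.9.1 | Assessments at days 90, 180 and 360; neurological events surveyed at each visit |
| Section 16 | Day 90 |
| Section 16.2 | Day 90, death or withdrawal of consent |

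Table 1 does not separate serious from non-serious events. Because non-serious recording ends by day 7, the marks at 3 months and later can, by inference, only be for SAEs.

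**2. Does any sentence settle it?** The statement that 24-hour reporting covers all study phases does not, because where the study ends is the point in dispute. No passage ranks one section above another.

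**3. Length of the gap**

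- Nominal: (365 − 90) / 365 = 275 / 365 = 75.3%.
- If the 3-month visit sets the cutoff (± 14 days, taken as days 76 to 104): (365 − 104) / 365 = 261 / 365 = 71.5%, up to (365 − 76) / 365 = 289 / 365 = 79.2%.
- If the 12-month visit also sets the far end (± 35 days, so days 330 to 400): (330 − 104) / 330 = 226 / 330 = 68.5%, up to (400 − 76) / 400 = 324 / 400 = 81.0%.
- Up to the 180-day endpoint: (180 − 90) / 180 = 50.0%.
- Table 1 visits: the Adverse Events row has 6 marks (treatment, 24 hours, discharge/7 days, 3 months, 6 months, 1 year). Two of the 6 fall after the 90-day cutoff.

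**4. What is still captured after day 90 under the shorter rule**

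- Neurological events, through the visit survey in Section 5.9.1.
- SAEs that cause a missed visit, through Section 8.1.
- Deaths, as mRS 6 where the 180-day score is obtained.

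The most exposed group is therefore non-neurological SAEs that do not cause a missed visit.

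**5. What is not affected.** The primary safety outcome is death within 90 days (Section 7.5.1). The specific events listed in Section 5.9.3 have windows of 7 or 90 days. All lie within both rules, and no pre-specified safety outcome uses later SAEs.

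**The case against.** The strongest reply is that little depends on this. The primary endpoints are recruitment and 180-day follow-up, the safety outcomes stop at day 90, and what remains is a descriptive listing in a single-arm feasibility study of 50 patients. That is correct, and it limits the severity. It does not make the rule sound: Section 5.9.3 calls adverse events critical endpoints and promises a year of recording, and SAEs missed late may not be recoverable.

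A second reply is that most of the protocol points past day 90, so a site would have to ignore its own visit schedule to stop there. Section 5.9.3 also asks for assessment at scheduled visits without limiting it to neurological events. That sentence belongs to the 365-day side of the conflict, however, and does not override the explicit wording of Sections 16 and 16.2. It is fair to add that nothing in the document shows how likely a site is to stop early.

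Third, the Manual of Procedures, which was not available here, holds more detail of the monitoring plan and might give a working rule. It could reduce the practical harm, but it would not correct a protocol that states two rules. This is a reason to be more confident in the contradiction than in its consequence.

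Two smaller points stand. The percentages describe time, not events. And the 12-month visit may fall before day 365, while Section 5.9.1 says day 360, so the corrected wording needs care.

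**Conclusion.** The concern holds. Sections 16 and 16.2 contradict Section 5.9.3 on when SAE recording ends, and their 90-day end of study also conflicts with Section 4.4 and Table 1. Under the shorter rule, 275 of 365 days (75%) are not covered. The share is 72% to 79% if the timing of the 3-month visit sets the cutoff, and about 68% to 81% if the 12-month visit window is allowed to vary as well.

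The effect on results is confined to the descriptive SAE record after day 90 and to the reporting and review that depend on it. This rests on two assumptions: that some sites would apply Sections 16 and 16.2 as written, and that the late marks in Table 1 are for SAEs. The number of events at risk cannot be estimated from the document. The correction should be made, but no planned analysis changes because of it.

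**What to change.** In Section 16, replace the 90-day follow-up as the end of SAE recording with the 12-month (day 365) visit. In Section 16.2, replace the 90-day final visit in the same way and leave death and withdrawal of consent as they are. This brings both into line with Section 5.9.3, Section 4.4 and Table 1, and it carries the follow-up of unresolved events to the same date. Keep 90 days only as the window for the named safety endpoints.

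When redrafting, state whether day 365 or the date of the 12-month visit governs, since that visit may take place from day 330, and align the day 360 in Section 5.9.1. Table 1 needs no change once the end of study has this single meaning.

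The cost is two sentences and the matching case report form guidance. The 6- and 12-month visits already exist, so the added work is a few more SAE forms and medical-monitor notifications.

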### **16.1            *Serious Adverse Events***

An adverse event is considered serious if it is life-threatening, prolongs hospitalization, requires a re-hospitalization, inpatient hospitalization, results in significant disability, or leads to death. Additionally, an important medical event that may not result in death, be life-threatening, or require hospitalization may be considered a serious adverse event when, based upon appropriate medical judgment, the event may jeopardize the subject and may require medical or surgical intervention to prevent one of the outcomes listed in this definition. Examples of such medical events include (but are not limited to): allergic bronchospasm requiring intensive treatment in an emergency room or at home; blood dyscrasias or convulsions that do not result in inpatient hospitalization; or, the development of drug dependency or drug abuse. Serious adverse events should not be reported for hospitalization or prolonged hospitalization in the following scenarios: for a diagnostic or elective surgical procedure related to a pre-existing condition; to allow for an efficacy measure for the study; or, for a planned surgical procedure that was not the result of a condition worsening due to participation in the study.

An assessment should be made regarding the seriousness, severity and relationship to the investigational devices and investigational procedure. The following factors should be considered when evaluating causality of adverse events: 1) the temporal sequence from the study procedure; 2) patient's response after discontinuation or re-introduction; and, 3) severity of the event. The investigators, on the basis of their clinical judgment and guided by the following definitions, should determine the relationship of an adverse event to the administration of the investigational device, and/or study procedure(s) as: definitely related, i.e. following in a reasonable temporal sequence, known to be a complication, and having no other explanation; probably related, i.e. following in a reasonable temporal sequence and not reasonably explained by the patient's clinical state or other therapies; possibly related, i.e. could have been explained by other therapies or patient's clinical state; or not related.

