### ***Secondary Endpoints:***

- Stroke Impact Scale – Mobility at 180 days
- Stroke Impact Scale – ADLs at 180 days
- EQ-5D-5L at 180 days
- Length of hospital stay
- Clinical Efficacy Endpoint: 180-day global disability assessed via the modified Rankin score (mRS), categorized as either mRS  $\leq 3$  or mRS  $> 3$
- Technical Efficacy Endpoint: Rate of surgical success
  - Predominantly or Only ICH: Reduction to  $< 15$  cc total volume AND  $>60\%$  reduction in hemorrhage volume on immediate post-treatment CT scan
  - Predominantly or Only IVH: mGraeb score of  $\leq 5$  on day 7 CT scan
- Safety Endpoint: Rate of mortality at 90 days

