#### **Statistical Analysis of Secondary Outcomes**

Secondary efficacy analyses will include 180-day global disability assessed via mRS, analyzed as the proportion of patients achieving mRS of 0-3. Two-sided 95% confidence intervals will be calculated for the proportion of subjects with mRS scores of 0-3 at the 180-day follow-up visit using the exact binomial distribution. The Kaplan-Meier Curve will be generated to assess the 90 day mortality. With the date of enrollment set at day 0, and any death occurring on or before day 90 will be included as a death.

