### **7.5 *Safety Analysis***

#### **7.5.1 *Safety Outcomes***

##### **Safety outcomes**

Several specific adverse events are monitored throughout the study. However the primary safety outcome to be assessed at completion of the trial will be death within 90 days.

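### Section 16.1 makes site-judged attribution part of the SAE definition for planned operations, so a scheduled, non-emergency re-operation blamed on the original hemorrhage may go unreported as an SAE

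*Combined protocol and SAP*

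**What the plan says.** Three parts of the protocol define what is reported, and they differ.

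- **Section 5.9.3** sets the scope broadly: "All serious adverse events occurring during the 365 days of study participation will be recorded". One ground for seriousness is that the event "requires or prolongs hospitalization". The attending physician then classifies causality, and unrelated is one of the categories.
- **Section 16** (introduction) says that a pre-existing condition does not count unless it worsens during the study. It does not ask why it worsened. It also closes the recording of non-serious events at hospital discharge or 7 days, whichever is earlier. Section 16.2 repeats that window.
- **Section 16.1** adds exemptions: "Serious adverse events should not be reported for hospitalization or prolonged hospitalization in the following scenarios". The last of them is a hospitalization "for a planned surgical procedure that was not the result of a condition worsening due to participation in the study".

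Section 16.1 also lets an important medical event be considered serious if it "may require medical or surgical intervention to prevent one of the outcomes listed in this definition". The pre-specified safety outcome is separate from all of this. Section 7.5.1 states that "the primary safety outcome to be assessed at completion of the trial will be death within 90 days".

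**The concern.** An SAE definition normally asks whether something happened, and relatedness is rated afterwards. The 16.1 clause reverses that order for planned operations. If the site decides that the hemorrhage and not study participation caused the worsening, the hospital stay is no longer a ground for reporting.

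The study has one arm and is unblinded (Section 7.6), and the investigator judges relatedness (Sections 16 and 16.1). Without a control group, the natural course of the bleed and an effect of the procedure cannot be separated in a single patient. The judgement that decides reporting is therefore one that nobody can check afterwards.

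What is at stake is the completeness of the SAE listing and of any count of re-operations. Section 5.9.3 calls adverse events critical endpoints, and the medical monitor's review under Section 16.2 starts from reported serious events.

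**Working it through.** The documents state no re-operation rate, SAE rate or threshold tied to this rule, so there is no figure of the plan's own to reproduce. The check is mainly textual.

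**1. Does the exemption reach operations arranged after enrollment?** The clause does not say that the procedure must have been planned before enrollment. Its qualifier also points the other way: an operation already planned at enrollment could not result from worsening due to participation. The qualifier has work to do only for operations arranged later.

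**2. Same event, three rules.** Take a scheduled, non-emergency shunt after discharge that the site attributes to the original bleed.

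| Rule | Result |
|---|---|
| Section 5.9.3 | SAE, because it requires hospitalization; causality rated afterwards |
| Section 16 | Worsening during the study counts, whatever the cause |
| Section 16.1 | Not an SAE on the hospitalization ground |

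Two sites could handle this event differently, each following the protocol.

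**3. Would another route catch it?**

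- *Listed events (Sections 5.9.3 and 7.5.2.1).* Symptomatic re-hemorrhage and ischemic stroke need the stated NIHSS or GCS change lasting 24 hours, emergency decompression, or death. The edema category is tied to emergency decompression. The surgical-complication category covers infection, abscess, meningitis and anesthetic complications. Section 5.5 names hydrocephalus as a complication to look for on the control CT, but it is not a listed event. The shunt meets none of these.
- *Other seriousness criteria.* The event stays serious if it is life-threatening, disabling or fatal. The important-medical-event route in 16.1 is available but discretionary.
- *Non-serious AE form.* Closed after day 7 or discharge.
- *Visit question (Section 5.9.1).* Patients or their representatives are asked about interim neurosurgical procedures. No section says that the answer goes to the medical monitor or the DSMB.

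The event can therefore pass through every route without being reported.

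**4. Size.** Input: N = 50 (Section 7.1). One omitted patient changes a proportion by 1/50 = 2 percentage points. The counts below are assumptions that show the range. Intervals are exact binomial 95%, the type Section 7.2 uses for its proportions.

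| Assumed true count | None omitted | One omitted | Two omitted |
|---|---|---|---|
| 5/50 | 10% (3.3 to 21.8) | 4/50 = 8% (2.2 to 19.2) | 3/50 = 6% (1.3 to 16.5) |
| 10/50 | 20% (10.0 to 33.7) | 9/50 = 18% (8.6 to 31.4) | 8/50 = 16% (7.2 to 29.1) |

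**5. Effect on the safety endpoint.** The synopsis gives "Safety Endpoint: Rate of mortality at 90 days", and Section 7.2 counts deaths without an attribution test: "any death occurring on or before day 90 will be included as a death". A rule about hospitalization cannot alter that count, so the change is 0.

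**The case against.** A reader might infer that re-operations blamed on the bleed are never reported, or that the trial's safety rate is biased downward. The documents support neither reading.

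- The pre-specified safety outcome is death within 90 days from any cause, and no re-operation rate or overall SAE rate is a pre-specified endpoint.
- The exemption removes only the hospitalization ground, and only for planned procedures. An emergency re-operation is not planned.
- The listed re-hemorrhage event includes growth of the existing bleed and can be met by neurological worsening alone. A symptomatic re-bleed that meets the definition and is later evacuated on schedule is still captured, whatever it is blamed on.
- Section 5.9.3 also counts any event that the treating clinician judges a significant hazard.
- The DSMB's review is not confined to SAEs. Section 7.5.2.1 sends it reports of all AEs and SAEs, and Section 9 has it review all adverse events.

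All of this stands, and it narrows the point considerably. It does not close the gap. The discretionary routes depend on the same site's judgement. The DSMB's access to non-serious events helps only while those events are being recorded, which ends at day 7 or discharge. The visit question gathers the information, but no section says where it goes.

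**Conclusion.** The point holds in a narrow form. Section 16.1 conflicts with Section 5.9.3 and with the introduction to Section 16. A planned, non-emergency neurosurgical procedure arranged after enrollment and attributed to the original hemorrhage may be left out of the SAE record if it meets no other seriousness criterion and no listed event. After day 7 or discharge it would not be recorded as a non-serious event either.

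SAE and re-operation counts could be understated by 2 percentage points per omitted patient at N=50. How many patients that might be is unknown, because the documents give no frequency for such procedures. A large fall in the rate would require several such operations, all attributed to the bleed and all missed by every other route, and nothing in the documents supports assuming that. The 90-day mortality result is untouched. This is a cheap improvement to safety reporting and does not undermine the trial's safety endpoint.

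**What to change.** Reconcile Sections 5.9.3, 16 and 16.1. In 16.1, limit the planned-procedure exemption to procedures already planned before enrollment and delete the attribution condition. State that any other neurosurgical procedure that requires or prolongs hospitalization is reported as an SAE, with relatedness rated separately. The neighbouring exemption for elective surgery related to a pre-existing condition needs the same limit, since the hemorrhage itself precedes enrollment.

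The visit question in Section 5.9.1 already collects the information, so no new assessment is needed. The cost is an edit to one clause and its neighbour, a few more SAE forms, and a slightly less favourable SAE count.
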